#### **10.4.1.3 Adverse event of special interest**

An AESI is an AE (serious or nonserious) of scientific and medical concern specific to the Sponsor's product or program, for which ongoing monitoring and immediate notification by the Investigator to the Sponsor is required. Such events may require further investigation in order to characterize and understand them. Adverse events of special interest may be added, modified or removed during a study by protocol amendment.

For these AESIs, the Sponsor will be informed immediately (ie, within 24 hours), per SAE notification described [Section 10.4.4](#), even if not fulfilling a seriousness criterion, using the corresponding pages in the CRF (to be sent) or screens in the eCRF.

- Anaphylactic reactions, systemic allergic reactions that require treatment (refer to [Appendix J](#) for Definition of Anaphylaxis)
- Severe ISRs that last longer than 24 hours

Note: A severe ISR (for AE reporting) is any event that meets one of the following criteria:

- With a diameter of at least 10 cm.
- Impacting daily activities.
- With ulceration or necrosis.
- For which operative intervention is required.
- Any infection meeting at least one of the following criteria:
  - Any serious infection (SAE).

- Requires parenteral (IV, intramuscular, SC) antimicrobial therapy  
Note: Antimicrobial therapy refers to antibiotic, antiviral, and antifungal agents.
- Requires oral antimicrobial therapy for longer than 14 days.
- Is a parasitic infection.
- Is an opportunistic infection (see [Appendix I](#)).
- Significant ALT elevation (see [Appendix H](#))
  - ALT  $>3$  x the ULN associated with total bilirubin  $>2$  x ULN; or
  - ALT  $>5$  x ULN if baseline ALT  $\leq 2$  x ULN; or
  - ALT  $>8$  x ULN and baseline  $>2$  x ULN.
- Malignancy
- Pregnancy occurring in a female patient enrolled in a study or in a female partner of a male patient enrolled in the study with IMP/NIMP. It will be qualified as an SAE only if it fulfills one of the seriousness criteria (see [Section 10.4.1.2](#)).
  - In the event of pregnancy in a female participant, IMP should be discontinued.
  - Follow-up of the pregnancy in a female participant or in a female partner of a male participant is mandatory until the outcome has been determined.
- Symptomatic overdose (serious or nonserious) with IMP/NIMP
  - An overdose (accidental or intentional) with the IMP is an event suspected by the Investigator or spontaneously notified by the patient and defined as at least twice the intended dose during an interval of  $<8$  days. The circumstances (ie, accidental or intentional) should be clearly specified in the verbatim and symptoms, if any, entered on separate AE forms.
  - An overdose (accidental or intentional) with any NIMP is an event suspected by the Investigator or spontaneously notified by the patient and defined as at least twice the maximum daily dose as specified in a drug label, within the intended therapeutic interval. The circumstances (ie, accidental or intentional) should be clearly specified in the in the overdose form and symptoms, if any, entered on separate AE forms.
  - Of note, asymptomatic overdose has to be reported as a standard AE.

#### **10.4.2 Serious adverse events waived from expedited regulatory reporting to regulatory authorities**

Not applicable.

#### **10.4.3 General guidelines for reporting adverse events**

- All AEs, regardless of seriousness or relationship to IMP/NIMP, spanning from the signature of the ICF until the end of the study as defined by the protocol for that patient, are to be recorded on the corresponding page(s) or screen(s) of the eCRF.

- When a safety event is categorized as a primary outcome, the event will be reported as an AE but will be waived from reporting to regulatory authorities provided an agreement has been reached with them.
- Whenever possible, diagnosis or single syndrome should be reported instead of symptoms. The Investigator should specify the date of onset, intensity, action taken with respect to IMP, corrective treatment/therapy given, additional investigations performed, outcome, and his/her opinion as to whether there is a reasonable possibility that the AE was caused by the IMP or by the study procedure(s). In studies that require the use of combined/multiple IMPs/NIMPs, the GSO with input from other appropriate study team members must determine if the causal relationship will either be assessed for the combined product as a regimen or as distinct entities. The GSO must communicate this decision to the study team for inclusion in the protocol and AE CRF.
- The Investigator should take appropriate measures to follow all AEs until clinical recovery is complete and laboratory results have returned to normal, or until progression has been stabilized, or until death, in order to ensure the safety of the patients. This may imply that observations will continue beyond the last planned visit per protocol, and that additional investigations may be requested by the monitoring team up to as noticed by the Sponsor. Patients who experience an ongoing SAE or an AESI, at the prespecified study end-date, should be followed until resolution, stabilization, or death and related data will be collected. The duration of poststudy follow-up and reporting of AEs will be specified (eg, until AE CRF).
- When treatment is prematurely discontinued, the patient's observations will continue until the end of the study as defined by the protocol for that patient.
- Laboratory, vital signs or ECG abnormalities are to be recorded as AEs only if:
  - Symptomatic and/or
  - Requiring either corrective treatment or consultation, and/or
  - Leading to IMP discontinuation or modification of dosing, and/or
  - Fulfilling a seriousness criterion, and/or
  - Defined as an AESI

**Table 4** summarizes the reporting timelines:

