#### \* Definition of Loss of Asthma Control

Loss of asthma control (LOAC) event during the treatment period is a deterioration of asthma defined as any of the following:

- A 30% or greater reduction from baseline in morning PEF on 2 consecutive days
- $\geq 6$  additional reliever puffs of salbutamol/albuterol or levosalbutamol/levalbuterol in a 24 hour period (compared to baseline) on 2 consecutive days
- Increase in ICS  $\geq 4$  times the last prescribed ICS dose (or  $\geq 50\%$  of the prescribed ICS dose at V2 if background therapy withdrawal completed)
- Requiring use of systemic (oral and/or parenteral) steroid treatment
- Requiring hospitalization or emergency room visit.

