#### **8.2.2 Reliever medication**

The reliever medication will not be dispensed or supplied by the Sponsor.

Patients may administer albuterol/salbutamol or levalbuterol/levosalbutamol MDI as reliever medication as needed during the study. Nebulizer solutions may be used as an alternative delivery method.

The description of the criterion for qualifying an asthma exacerbation event based on nebulizer using, will use the nebulizer-to-puff conversion factor for application to loss of asthma control (LOAC) definition.

Salbutamol/albuterol nebulizer and levosalbutamol/levalbuterol nebulizer use will be converted as shown on the following tables:

Salbutamol/Albuterol Nebulizer Solution -Total Daily Dose (mg)	Number of Puffs*
2.5	4
5.0	8
7.5	12
10	16

\*Conversion factor: salbutamol/albuterol nebulizer solution (2.5 mg) corresponds to 4 puffs

- Example of salbutamol/albuterol nebulizer-to-puff Conversion: Patient received 3 salbutamol/albuterol nebulizer treatments (2.5 mg/treatment) between 7 and 11 AM. Total daily = 7.5 mg or 12 puffs

Levosalbutamol/Levalbuterol Nebulizer Solution -Total Daily Dose (mg)	Number of Puffs*
0.63	2
1.25/1.26	4
1.89	6
2.5/2.52	8
3.15	10
3.75/3.78	12
5/5.04	16

\*Conversion factor: levosalbutamol/levalbuterol nebulizer solution (1.25 mg) corresponds to 4 puffs

- Example of levosalbutamol/levalbuterol nebulizer-to-puff Conversion: Patient received 3 levosalbutamol/levalbuterol nebulizer treatments (1.25 mg/treatment) between 7 and 11 AM. Total daily = 3.75 mg or 12 puffs.

After conversion of nebulizer-to-puff, and for every instance, where the number of puffs is  $\geq 6$  additional puffs of salbutamol/albuterol or levosalbutamol/levalbuterol in a 24-hour period (compared to Baseline) on 2 consecutive days in any week, a LOAC event should be documented.

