## 9 ASSESSMENT OF INVESTIGATIONAL MEDICINAL PRODUCT

### 9.1 PRIMARY ENDPOINT

The primary endpoint is the proportion of patients with LOAC (for definition, see [Section 5](#)).

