### **10.3.3 List of criteria for permanent treatment discontinuation**

The patients may withdraw from treatment with the IMP if they decide to do so, at any time and irrespective of the reason, or this may be the Investigator's decision. All efforts should be made to document the reason(s) for treatment discontinuation and this should be documented in the eCRF.

Patients must be withdrawn from the study treatment for the following reasons:

- At their own request or at the request of their legally authorized representative (legally authorized representative means an individual or judicial or other body authorized under applicable law to consent on behalf of a prospective patient to the patient's participation in the procedure(s) involved in the research).
- If, in the Investigator's opinion, continuation in the study would be detrimental to the patient's well-being.
- At the specific request of the Sponsor.
- In the event of a protocol deviation, at the discretion of the Investigator or the Sponsor.
- Pregnancy.

- Loss of asthma control: Patients will be instructed to contact the Investigator if a patient feels that his or her asthma is not adequately controlled (clinical exacerbation, intolerable or incapacitating symptoms, frequent nocturnal awakenings, frequent albuterol or levalbuterol use).

If a patient meets the criteria for a LOAC at any time during the 12-week IMP treatment period, he/she will be permanently withdrawn from IMP treatment and treated by the Investigator with standard of care according to standard medical practice.

- Anaphylactic reactions or systemic allergic reactions that are related to IMP and require treatment (see [Appendix J](#)).
- Diagnosis of a malignancy during study, excluding squamous or basal cell carcinoma of the skin.
- Any situation that meets permanent discontinuation rule as outlined in [Appendix H](#). ‘General Guidance for the follow-up of laboratory abnormalities by Sanofi’.
- Any opportunistic infection, such as TB or other infections whose nature or course may suggest an immunocompromised status (see [Appendix I](#)).
- Serum ALT >3 ULN and total bilirubin >2 ULN (see [Appendix H](#)).
- Serum ALT >5 ULN if baseline ALT ≤2 ULN or ALT >8 ULN if baseline ALT >2 ULN (see [Appendix H](#)).

Any abnormal laboratory value or ECG parameter will be immediately rechecked for confirmation before making a decision of permanent discontinuation of the IMP for the concerned patient.

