## **10.4 OBLIGATION OF THE INVESTIGATOR REGARDING SAFETY REPORTING**

### **10.4.1 Definitions of adverse events**

#### **10.4.1.1 Adverse event**

An AE is any untoward medical occurrence in a patient or clinical investigation patient administered a pharmaceutical product and which does not necessarily have to have a causal relationship with this treatment.

Asthma exacerbations should only be reported as AEs if they fulfill a seriousness criterion.

For this study, asthma exacerbations should be managed by the Investigators based on their medical judgment and applicable national/international asthma management guidelines.

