2.4.5.1 Analyses of adverse events

Generalities

The primary focus of adverse event reporting will be on TEAEs. Pre-treatment and post-treatment adverse events will be described separately.

If an adverse event date/time of onset (occurrence, worsening, or becoming serious) is incomplete, an imputation algorithm will be used to classify the adverse event as pre-treatment, treatment-emergent, or post-treatment. The algorithm for imputing date/time of onset will be conservative and will classify an adverse event as treatment emergent unless there is definitive information to determine it is pre-treatment or post-treatment. Details on classification of adverse events with missing or partial onset dates are provided in [Section 2.5.3](#).

Adverse event incidence tables will present the number (n) and percentage (%) of patients experiencing an event by treatment group. Multiple occurrences of the same event in the same patient will be counted only once in the tables within a treatment phase. The denominator for computation of percentages is the safety population within each treatment group. Sorting will be based on results for the SAR440340 and dupilumab coadministration group by the following orders:

- Tables presented by SOC: sorted by internationally agreed SOC order
- Tables presented by PT: sorted by decreasing frequency of PT
- Tables presented by SOC and PT: sorted by internationally agreed SOC order and decreasing frequency of PT within SOC
- Tables presented by SOC, HLGT, HLT, and PT: sorted by internationally agreed SOC order and then alphabetical order of HLGT, HLT, and PT

Analysis of all TEAEs

The following TEAE summaries will be generated for the safety population.

- Overview of TEAE, summarizing number (%) of patients with any
 - TEAE
 - Severe TEAE
 - Serious TEAE
 - TEAE leading to death
 - TEAE leading to permanent treatment discontinuation
- All TEAEs by primary SOC
- All TEAEs by primary SOC, HLGT, HLT, and PT
- All TEAEs by primary SOC and PT
- All TEAEs by PT
- All TEAEs related to SAR440340 or matching placebo by primary SOC, HLGT, HLT and PT
- All TEAEs related to dupilumab or matching placebo by primary SOC, HLGT, HLT and PT
- All TEAEs by maximal severity, presented by primary SOC and PT
- Listing of all TEAEs

Analysis of all treatment emergent SAEs

- All treatment-emergent SAEs by primary SOC, HLGT, HLT, and PT
- All treatment-emergent SAEs by primary SOC and PT
- All treatment-emergent SAEs by PT

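### The protocol does not say whether a non-serious loss of asthma control is an adverse event, so the efficacy difference can leak into the tolerability tables

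*Protocol*

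**What the plan says.** Protocol 10.4.1.1, within the definition of an adverse event, says: "Asthma exacerbations should only be reported as AEs if they fulfill a seriousness criterion".

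Protocol 10.4.3, the general reporting guidance, asks sites to record "All AEs, regardless of seriousness or relationship to IMP/NIMP, spanning from the signature of the ICF until the end of the study". It then adds: "When a safety event is categorized as a primary outcome, the event will be reported as an AE". That second instruction carries no seriousness condition. Its trigger is a safety event that has been categorized as a primary outcome.

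Protocol 9.1 names the primary outcome: "The primary endpoint is the proportion of patients with LOAC". Under Protocol 10.3.3, a patient who meets the LOAC criteria during the 12-week treatment period must stop study drug: "he/she will be permanently withdrawn from IMP treatment".

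SAP 2.4.5.1 tabulates all TEAEs, and its overview includes a row for "TEAE leading to permanent treatment discontinuation". It gives no rule to exclude, flag or separately present LOAC or asthma-worsening terms.

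**The concern.** For a non-serious LOAC, the two reporting instructions can lead to different entries in the case report form, and the protocol gives no order of precedence. Individual sites (up to about 80 are planned) would settle the question, not the analysts. The SAP's blinded medical review decides LOAC status for efficacy. It does not decide whether the same event is an AE.

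Safety and tolerability is a secondary objective. If LOAC enters the AE data, the placebo arm carries more of it simply because the treatments are expected to prevent it. The any-TEAE row and the discontinuation row would then partly restate the primary efficacy result. A real excess of other adverse events on an active arm could be offset. If only some sites enter LOAC, the size of this effect could not be read from the summary rows.

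**Working it through.** **Step 1. Does the exemption in 10.4.1.1 clearly cover every LOAC component?**

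| LOAC component | Serious by itself? | Clearly an exacerbation? |
|---|---|---|
| Morning PEF fall of 30% or more on 2 days | No | Not stated |
| 6 or more extra reliever puffs on 2 days | No | Protocol 8.2.2 suggests so |
| Large ICS increase | No | Not stated |
| Systemic steroid | No | Matches the SAP's pre-study definition |
| Hospitalization or emergency room visit | Admission yes; emergency visit not automatically | Matches the SAP's pre-study definition |

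The terms overlap. Protocol 8.2.2 introduces the nebulizer conversion used for LOAC with "The description of the criterion for qualifying an asthma exacerbation event based on nebulizer using". The SAP's definition of exacerbation (section 2.1.1) applies only before the study and uses systemic steroid, hospitalization or emergency care. The LOAC list includes "Requiring use of systemic (oral and/or parenteral) steroid treatment", which alone meets no seriousness criterion. So a steroid-treated outpatient LOAC falls within 10.4.1.1 if it is called an exacerbation, and within 10.4.3 if it is called a safety event that is the primary outcome. A LOAC based only on PEF may fall outside the exemption altogether.

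**Step 2. Planning rates (Protocol 11.1).** Placebo 40%, SAR440340 14%, two-sided 5%, 80% power, 15% dropout. The stated size is reproduced. A two-proportion calculation gives 45 per group without continuity correction and 52 with it. At 50 per group, power is 84.4% or 78.1% respectively. Dropout gives 50 / (1 - 0.15) = 58.8, against 60 stated. The sample size is not in dispute; only the rates are used here. Expected LOAC per 60 patients: 60 x 0.40 = 24 on placebo and 60 x 0.14 = 8.4 on SAR440340.

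**Step 3. TEAEs leading to permanent discontinuation.** Let f be the share of LOAC entered as AEs (unknown, 0 to 1). Let b be the rate of other TEAE discontinuations, equal in both arms and independent of LOAC. Assume all LOAC is non-serious and every LOAC entered counts in this row. The row rate is 1 - (1 - b)(1 - f p), so the placebo excess is (1 - b) x f x (0.40 - 0.14).

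| b (assumed) | f | Placebo | SAR440340 | Gap, points |
|---|---|---|---|---|
| 0% | 1 | 40.0% | 14.0% | 26.0 |
| 2% | 0.5 | 21.6% | 8.9% | 12.7 |
| 2% | 1 | 41.2% | 15.7% | 25.5 |
| 5% | 0.5 | 24.0% | 11.7% | 12.3 |
| 5% | 1 | 43.0% | 18.3% | 24.7 |

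At f = 0 the gap is zero. Serious LOAC is an AE under either rule. If 10% of LOAC were serious (assumed), the part that depends on the unclear rule would be at most 0.9 x 26 = 23.4 points.

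**Step 4. Any TEAE.** Let r be the non-asthma TEAE rate, equal in both arms and independent of LOAC. The rate is 1 - (1 - r)(1 - f p) and the gap is (1 - r) x f x 0.26.

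| r (assumed) | f | Placebo | SAR440340 | Gap, points |
|---|---|---|---|---|
| 40% | 0.5 | 52.0% | 44.2% | 7.8 |
| 40% | 1 | 64.0% | 48.4% | 15.6 |
| 55% | 1 | 73.0% | 61.3% | 11.7 |
| 70% | 0.5 | 76.0% | 72.1% | 3.9 |
| 70% | 1 | 82.0% | 74.2% | 7.8 |

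**Step 5. What could be hidden.** At f = 1 the any-TEAE rates are equal when the SAR440340 non-asthma rate is x = 1 - (1 - r)(0.60 / 0.86). For r = 40%, x = 58.1%, so a true excess of 18.1 points would not show in that row. For r = 70%, x = 79.1%, an excess of 9.1 points.

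**Step 6. What one rule changes.** If non-serious LOAC is never an AE, it adds nothing to any arm. If it always is, the ceiling gap remains but is known to be the efficacy effect. Either way the variation between sites disappears.

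**The case against.** The best counter-argument is that the protocol already implies an answer. The trigger in 10.4.3 is a safety event, whereas the protocol consistently treats LOAC as efficacy: sections 4.7 and 6.5 call it the primary efficacy variable, and the flow chart places LOAC reporting under Efficacy, apart from AE reporting. Section 10.4.1.1 is the specific text and 10.4.3 the general one. The regulatory waiver in the same bullet makes most sense for serious events, on which the two sections agree. All of this stands, and it rules out calling the two sections a flat contradiction, as a reader might. But none of it is stated as a rule, and 10.4.1.1 speaks of exacerbations, not LOAC.

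A reader might also see a second conflict in 10.4.2, which marks waived serious events as not applicable. The documents do not support that: the waiver in 10.4.3 is conditional on an agreement with the authorities, so both can hold.

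The effect would also be partly visible. The SAP gives TEAEs and TEAEs leading to discontinuation by preferred term with listings, and disposition by main reason. Safety is descriptive, so no error rate is involved. Site staff other than dose preparers are blinded, so reporting habits should not differ by arm. These points limit the harm. They do not remove it, because the distortion needs only unequal LOAC incidence, and the summary rows would still mix the two kinds of event.

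**Conclusion.** The concern holds as an unresolved reporting instruction that can carry the efficacy effect into two descriptive safety rows, in favour of the active arms. The size runs from zero to a ceiling of about 26 points for TEAEs leading to discontinuation, and from zero to about 16 points for any TEAE.

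These figures rest on the planning rates, on all LOAC being non-serious, on each LOAC entered counting as a discontinuation TEAE, and on assumed other-event rates that are equal across arms and independent of LOAC. The share of LOAC entered as AEs is not in the documents, so 26 points should not be read as an expected bias. The 14% is stated for SAR440340 only; no planning rate is given for the coadministration arm. Tables of serious events are unaffected, since both sections capture them.

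**What to change.** Reconcile Protocol 10.4.1.1 and 10.4.3 into one AE-reporting rule that names LOAC and covers each of its components. One example is to record non-serious LOAC only as an efficacy event and serious events as AE/SAE. Issue it by amendment or site letter, to all sites at the same time.

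In SAP 2.4.5.1, present any TEAE and TEAEs leading to permanent discontinuation with and without asthma-worsening terms, and fix the list of terms before unblinding. This second part is needed even with a single rule, because uniform reporting of LOAC as an AE would leave the gap at its largest.

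The cost is about one sentence of protocol text or a letter, plus one additional table. Treatment, endpoints and sample size do not change.

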#### **10.4.6 Guidelines for management of specific laboratory abnormalities**

Decision trees for the management of certain laboratory abnormalities by Sanofi are provided in [Appendix H](#).

The following laboratory abnormalities should be monitored, documented, and managed according to the related flow chart in protocol appendices.

- Neutropenia
- Thrombocytopenia
- Increase in ALT
- Increase in serum creatinine
- Increase in CPK

Note: In some clinical trials these laboratory abnormalities can be considered as AESIs. For this study, only significant ALT increase will be considered as AESIs (see [Section 10.4.1.3](#))

In addition, on treatment eosinophil counts  $>3000/\text{mm}^3$  (3.0 giga/L) (confirmed by retest) are to be reported as AEs.

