#### **10.6.4 Elevated liver function tests**

No preclinical and clinical data has suggested any hepatic toxicity of SAR440340 or dupilumab; however, as a general consideration of clinical development, the administration of immunosuppressant or immunomodulating agents may represent an additional risk factor for hepatotoxicity.

In order to closely follow liver function tests (LFT), assessment of total protein, albumin, total bilirubin (in case of values above the normal range, differentiation in conjugated and nonconjugated bilirubin), alanine aminotransferase, aspartate aminotransferase, and alkaline phosphatase are measured as part of the clinical laboratory testing.

Guidance for the investigation of elevated LFTs as well as concurrent management of IMP is provided in [Appendix H](#).

Alanine transaminase elevations defined in [Section 10.4.1.3](#) should be reported as AESIs with immediate notification.

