2.4.5.3 Analyses of laboratory variables

The summary statistics (including number, mean, median, Q1, Q3, SD, minimum and maximum) of all laboratory variables (central laboratory values and changes from baseline) will be calculated for each visit or study assessment (baseline, each post-baseline time point, and last on-treatment) by treatment group. For each continuous parameter listed in [Section 2.1.4.3](#), mean changes from baseline with the corresponding standard error will be plotted over time in each treatment group. This section will be organized by biological function as specified in [Section 2.1.4.3](#).

The incidence of PCSAs (list provided in [Appendix A](#)) at any time during the TEAE period will be summarized by biological function and treatment group whatever the baseline level and/or according to the following baseline status categories:

- Normal/missing
- Abnormal according to PCSA criterion or criteria

For parameters for which no PCSA criteria are defined, similar table(s) using the normal range will be provided.

Laboratory measurements obtained at either scheduled or unscheduled visits will be used in analyses of PCSA. In addition, both centralized and local test results will be used. Centralized data will be used preferentially to the local measures in the analysis when several measurements are performed on the same date and at the same time for a given laboratory test.

Listings will be provided with flags indicating the out of range values as well as the PCSA values.

Potential drug-induced liver injury

If there is any imbalance in the incidence of liver-related adverse events across the treatment groups, the following analysis of liver-related adverse events will be performed.

The liver function tests, namely AST, ALT, alkaline phosphatase, and total bilirubin will be used to assess possible drug-induced liver toxicity. The proportion of patients with PCSA values at any post-baseline visit will also be displayed by duration of exposure for each treatment group.

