Time to onset of the initial ALT and AST elevation ($>3 \times \text{ULN}$) and total bilirubin elevation ($>2 \times \text{ULN}$) will be analyzed using Kaplan-Meier estimates presented by treatment group. A graph of distribution of peak values of ALT versus peak values of total bilirubin will also be presented on a logarithmic scale. The graph will be divided into 4 quadrants with a vertical line corresponding to $3 \times \text{ULN}$ for ALT and a horizontal line corresponding to $2 \times \text{ULN}$ for total bilirubin.

Listings of selected laboratory parameters for possible Hy's law cases identified by treatment group (eg, patients with any elevated ALT $>3 \times \text{ULN}$, and associated with an increase in bilirubin $\geq 2 \times \text{ULN}$) will be provided.

The normalization (to $\leq 1 \times \text{ULN}$) or return to baseline (if baseline is $>\text{ULN}$) of elevated liver function tests will be summarized by categories of elevation ($>3 \times \text{ULN}$, $>5 \times \text{ULN}$, $>10 \times \text{ULN}$, $>20 \times \text{ULN}$ for ALT and AST, $>1.5 \times \text{ULN}$ for alkaline phosphatase, and $>1.5 \times \text{ULN}$ and $>2 \times \text{ULN}$ for total bilirubin) with the following categories of normalization: never normalized, normalized despite treatment continuation of IMP, or normalized after IMP discontinuation. A patient will be counted only under the maximum elevation category.

Change in blood eosinophil

Mean changes from baseline in eosinophil count will be summarized and plotted (with corresponding standard error) over time in each treatment group for patients with baseline blood eosinophil $< 0.5 \text{ Giga/L}$ and patients with baseline blood eosinophil $\geq 0.5 \text{ Giga/L}$. Number (%) of patients with post-baseline peak blood eosinophil $\geq 1 \text{ Giga/L}$ and $< 3 \text{ Giga/L}$, $\geq 3 \text{ Giga/L}$ and $< 5 \text{ Giga/L}$, and $\geq 5 \text{ Giga/L}$ will also be summarized in each treatment group and by baseline blood eosinophil status (All, $< 0.5 \text{ Giga/L}$, $\geq 0.5 \text{ Giga/L}$).

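### The SAP's liver-injury analyses start only on an imbalance in liver adverse events, so an imbalance made up of isolated, unmanaged ALT or AST rises need not start them

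*Protocol*

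**What the plan says.** The part of SAP 2.4.5.3 on potential drug-induced liver injury opens with a condition: "If there is any imbalance in the incidence of liver-related adverse events across the treatment groups", the analyses that follow are done. They comprise:

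- PCSA proportions for the liver tests by duration of exposure;
- Kaplan-Meier analyses ("Time to onset of the initial ALT and AST elevation" above 3 × ULN, and the same for total bilirubin above 2 × ULN);
- a plot of peak ALT against peak bilirubin;
- a Hy's law listing ("Listings of selected laboratory parameters for possible Hy's law cases identified by treatment group");
- a summary of normalisation by category of elevation, on and off IMP.

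No laboratory finding is named as an alternative trigger. The closest definition of a liver event is in SAP Table 3, which searches reported AE terms with a narrow MedDRA query and does not use laboratory values.

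Protocol 10.4.3 decides which laboratory findings become AEs: "Laboratory, vital signs or ECG abnormalities are to be recorded as AEs only if" at least one of five conditions is met. Besides symptoms, seriousness and AESI status, these are "Requiring either corrective treatment or consultation, and/or" and "Leading to IMP discontinuation or modification of dosing, and/or". On AESI status, protocol 10.4.6 says: "For this study, only significant ALT increase will be considered as AESIs". Protocol 10.4.1.3 and Table 4 set the limits:

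- ALT above 5 × ULN if baseline is at most 2 × ULN;
- ALT above 8 × ULN if baseline is higher than that;
- ALT above 3 × ULN together with total bilirubin above 2 × ULN.

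**The concern.** The analyses describe laboratory elevations from 3 × ULN upwards, but their trigger reads a different data source with higher entry limits. Between the two lies a range of values that the analyses are designed to characterise and that the trigger may not see. Safety of SAR440340 alone and with dupilumab is a secondary objective. Protocol 10.6.4 notes that immunomodulating agents may add hepatotoxic risk and gives this as the reason to follow liver tests closely. If liver enzymes differed between arms mainly within that range, the SAP as written would not call for the outputs that show when the rises began, whether ALT and bilirubin peaked together, and whether values recovered on or off IMP.

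**Working it through.** The plan states no figure here to reproduce. The check takes each kind of elevation and asks whether it must become an AE (protocol 10.4.1.2, 10.4.1.3, 10.4.3, Table 4), whether it is in the unconditional PCSA tables (SAP 2.4.5.3, Appendix A), and whether it can start the conditional analyses. In rows 1, 2 and 5 the patient has no symptoms, consultation, treatment, IMP action or seriousness.

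| Case | Must be an AE? | In the PCSA tables? | Can start the liver analyses? |
|---|---|---|---|
| 1. ALT >3 to 5 × ULN, bilirubin ≤2 × ULN, baseline ALT ≤2 × ULN | No | Yes (>3 × ULN) | No |
| 2. ALT >3 to 8 × ULN, bilirubin ≤2 × ULN, baseline ALT >2 × ULN | No | Yes | No |
| 3. ALT >3 × ULN with bilirubin >2 × ULN | Yes: AESI, and on the list of medically important events | Yes, as a combined criterion | Yes |
| 4. ALT >5 × ULN, baseline ALT ≤2 × ULN | Yes: AESI | Yes | Yes |
| 5. AST alone >3 × ULN | No: AST has no AESI limit | Yes | No |

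Row 2 should concern few patients, because exclusion criterion E 39 removes anyone with ALT or AST above 3 × ULN at Visit 1. Row 1 is the main gap. Asymptomatic ALT counts as medically important by level alone only above 10 × ULN, so seriousness does not close rows 1 or 2.

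An arm difference made up only of rows 1, 2 and 5 can leave the liver AE counts equal, and the condition in SAP 2.4.5.3 is then not met.

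Illustration, using the planned 60 patients per arm. The counts are assumed, not predicted, and every affected patient is taken to be in row 1:

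- 8/60 (13.3%) on coadministration v 1/60 (1.7%) on placebo: Fisher exact two-sided p = 0.032.
- 6/60 (10.0%) v 0/60 (0%): p = 0.027.

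Both are compatible with 0 v 0 liver AEs. The p-values only show that such a difference would be large enough to want characterised. They say nothing about how likely it is.

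The following outputs do not depend on the condition:

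- PCSA incidence by arm, with ALT and AST at >3, >5, >10 and >20 × ULN, bilirubin at >1.5 and >2 × ULN, and the combined ALT >3 with bilirubin >2 × ULN;
- by-visit summaries and mean-change plots;
- listings flagging out-of-range and PCSA values;
- the shift tables promised in protocol 11.4.3.1.3.

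In both illustrations the ALT >3 × ULN row of the PCSA table would show the imbalance.

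**The case against.** The strongest reply is that little is lost. The unconditional outputs show the imbalance, the combined ALT and bilirubin criterion is a Hy's-law-type screen tabulated whatever the AE counts, and the listings let a reader trace onset and recovery patient by patient. The most serious elevations (rows 3 and 4) are AESIs and reach the AE data. The trigger is any imbalance, with no numerical threshold, so a few recorded cases in one arm could suffice. Safety analysis in this Phase 2a trial is descriptive, protocol 10.6.4 reports no hepatic signal for either drug, and an unblinded DMC reviews data under its own charter.

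Most of this stands, and it limits the size of the point. A reader might infer that asymptomatic ALT rises up to 5 × ULN never become AEs, so that a laboratory imbalance could not start the analyses. The documents do not support that: a rise that needs consultation or treatment, or leads to an IMP change, is an AE at any level. A reader might also infer that a laboratory liver signal would go unseen. That is not supported either, given the unconditional outputs.

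One uncertainty cannot be resolved. Protocol 10.4.6 sends ALT increases to a flow chart in Appendix H that is not shown in the text reviewed. If it calls for consultation at 3 to 5 × ULN, many row 1 cases would be AEs and the gap would shrink.

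The reply does not explain why analyses that start at 3 × ULN should depend on a data source that can omit values at that level. Patient listings are also no substitute for a prespecified comparison by arm.

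**Conclusion.** The point holds as a mismatch between a trigger and the data it should respond to. An imbalance in isolated, unmanaged ALT rises of >3 to 5 × ULN (to 8 × ULN if baseline exceeds 2 × ULN), or in isolated AST rises, need not start the liver-injury analyses. It would be visible elsewhere. What may be missing is the prespecified arm-level account of onset time, joint peak ALT and bilirubin, and recovery. The size is moderate: no efficacy result is touched, and the cases of greatest concern reach the AE data.

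Three assumptions matter: that the opening condition governs everything under the liver-injury subheading; that liver-related events are identified from reported AE terms, as in SAP Table 3; and that the unseen ALT flow chart does not turn most row 1 cases into AEs.

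**What to change.** In SAP 2.4.5.3, delete the AE-imbalance condition and produce the liver-injury outputs unconditionally from the laboratory data. Alternatively, extend the trigger to any post-baseline ALT or AST above 3 × ULN, or total bilirubin above 2 × ULN, in any arm. Either version also removes the reliance on an undefined degree of imbalance. The cost is one sentence in the SAP and a few standard safety outputs, some of which may be sparse. The data are already collected. No change to AE reporting or clinical management is proposed.
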